11.2 General aspects

Descriptive statistics will be based on means (+/- standard deviation) or medians [interquartile range] depending on the distribution of quantitative variables. Qualitative variables will be described in terms of numbers and percentages. Univariate comparisons will use the usual statistical tests after checking the distribution of the variables (Chi2 or Fisher's test, t-test, anova or their non-parametric equivalents Wilcoxon and Kruskal-Wallis tests). Paired sample tests will be used if necessary.

The tests will be performed at the 5% significance level. The 95% confidence intervals will be provided for each estimate.

The calculations will be done using SPSS v21 IBM and R software (version 3.6.1, <http://www.R-project.org>).

11.3 Main objective

The difference between the prevalences of global undernutrition between the HAS and GLIM groups will be compared using the McNemar test, designed for the comparison of proportions in matched samples.

11.4 Secondary objectives

11.4.1 Comparison of the prevalence of severe undernutrition

The difference between the prevalences of severe undernutrition between the HAS and GLIM groups will be compared using the test described in the main objective.

11.4.2 Comparison of morbidity and mortality

Morbidity and mortality will be compared between the HAS and GLIM groups, for moderate and severe undernutrition, by comparing the length of hospital stay, mortality and autonomy at discharge.

Length of stay in hospital

There is a relationship between the incidence of mortality and all length of stay variables. Length of stay will therefore be analysed using a competitive risk method, which takes into account the fact that patients who die are no longer eligible for length of stay analysis (25).

The estimator also provides the probability of in-hospital death, so that the probability of hospital discharge versus death at any time after inclusion in the study can be assessed simultaneously.

Mortality rate

The estimation of mortality rates will be carried out by the Kaplan and Meier method. The comparison of the 2 curves will be performed by a Logrank test. The mortality rates in the 2 groups will be estimated via the survival curves.

ADL

The ADL score will be compared between the 2 groups using the discrete numerical variable comparison tests described in the general aspects.

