1.8 Research hypothesis

We hypothesise that the prevalence of undernutrition in a population of patients hospitalised in diabetology-obesity, pneumology, oncology and gastro-nutrition, under 70 years of age is different according to the diagnostic criteria recommended by the French National Authority for Health or those recommended by the Global Leadership Initiative on Malnutrition. Moreover, these two definitions could have a different impact on the patient's morbidity and mortality. The choice of the method of assessment of muscle function could impact on this prevalence.

2 Originality of the research

The definitions used in the scientific literature to diagnose undernutrition in hospitalised patients are heterogeneous and make it difficult to compare populations within different studies. The international consensus on the definition of undernutrition could provide a solution to these limitations. The recommendation of a new definition of undernutrition in France, which differs on certain criteria from that of the international consensus, could lead to a different prevalence of undernutrition. To our knowledge, no study has assessed whether the

prevalence of undernutrition according to these two definitions is different in hospitalized patients. Furthermore, no study has assessed the prognostic character of undernutrition according to these two definitions on the morbidity and mortality of these patients. Muscle function plays an important role in these two definitions and different measurement tools are proposed. The predictive capacity of these different tools on undernutrition has never been evaluated or compared.

3 Objective

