3.2 Secondary objectives

The secondary objectives will be, for patients hospitalised in short stay and follow-up care and rehabilitation of diabetes-obesity, pneumology, oncology and gastro-nutrition:

- To compare the prevalence of severe undernutrition according to the HAS and GLIM diagnostic criteria ;
- To compare the morbidity and mortality of moderate and severe undernutrition according to the HAS and GLIM diagnostic criteria :
 - Length of stay ;
 - Mortality rate ;
 - Autonomy at discharge.
- To compare the predictive capacity of muscle function assessment tools on undernutrition according to the HAS and GLIM diagnostic criteria .

4 Outcome

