8.2 Diagnosis of undernutrition according to the GLIM criteria

The diagnosis of undernutrition will also be carried out in the framework of this research according to the GLIM criteria. It will be based on the search for at least 1 phenotypic criterion and 1 etiological criterion. Severe undernutrition will be based solely on phenotypic criteria. See detailed description in section 10.1.

This diagnosis according to the GLIM definition will be made by one of the investigators not involved in the management of the patient. The patient's team will be blinded to these results so as not to influence the management of the patient.

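### Section 11.4.2 compares mortality and ADL between HAS-positive and GLIM-positive patients with tests for independent groups, although the two groups share patients; the error is conservative and can hide a real difference.

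*Combined protocol and SAP*

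**What the plan says.** Section 8.2 adds a second diagnosis for the same patients: "The diagnosis of undernutrition will also be carried out in the framework of this research according to the GLIM criteria". Section 10.1 sets out both sets of criteria for the whole cohort. The only random draw (9.1.2) decides who is sampled; nobody is allocated to a definition.

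For the primary objective, section 11.3 treats the data as paired and chooses McNemar's test, intended for "the comparison of proportions in matched samples".

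Section 3.2 sets the secondary objective: "To compare the morbidity and mortality of moderate and severe undernutrition according to the HAS and GLIM diagnostic criteria". Section 11.4.2 carries it out as a contrast of two groups: "Morbidity and mortality will be compared between the HAS and GLIM groups, for moderate and severe undernutrition". For mortality, "The comparison of the 2 curves will be performed by a Logrank test". For autonomy, "The ADL score will be compared between the 2 groups using the discrete numerical variable comparison tests described in the general aspects". For length of stay it names a competing-risk method and says what the estimator yields, but no between-group test.

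Section 11.2 adds a general clause: "Paired sample tests will be used if necessary". No section says how a patient positive on both definitions is handled in 11.4.2.

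**The concern.** A patient positive on both definitions contributes the same death time and the same discharge ADL to both sides of the comparison. The log-rank test and the unpaired t or Wilcoxon tests compute their variance as if the two sides were separate people. With shared patients the two summaries are positively correlated, so the true variance of their difference is smaller than the test assumes.

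The consequence is lost power. Section 1.8 hypothesises that the two definitions may differ in their impact on morbidity and mortality, and section 2 presents this as new ground: "no study has assessed the prognostic character of undernutrition according to these two definitions". A non-significant result would be read as an answer to that question when overlap alone could have produced it.

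**Working it through.** **Inputs.** Section 11.4.2 gives no figure to reproduce. From 11.1: N = 260, HAS prevalence 34%, GLIM prevalence 49%. So HAS-positive H = 0.34 × 260 = 88.4 and GLIM-positive G = 0.49 × 260 = 127.4. The 260 is the size set for the primary comparison and serves here only as an input.

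**Feasible overlap.** Let a be the number positive on both. Because 34% + 49% is below 100%, a can be as low as 0; the maximum is 88.4. Chance agreement gives 0.34 × 0.49 × 260 = 43.3. The documents do not state a, so every row below is an assumption; 62.4 is an intermediate value.

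**Variance, in units of the outcome variance.**
- Assumed by the test: 1/H + 1/G = 0.01916 (SE 0.1384).
- True: 1/H + 1/G − 2a/(H·G).
- SE ratio r = √(assumed/true). Type I error of a nominal 5% test = 2 × (1 − Φ(1.96 r)).

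| Shared a | True variance | r | True type I error |
|---|---|---|---|
| 0 | 0.01916 | 1.00 | 5% |
| 43.3 | 0.01147 | 1.29 | 1.1% |
| 62.4 | 0.00808 | 1.54 | 0.25% |
| 88.4 | 0.00346 | 2.35 | 0.0004% |

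A null simulation of the named kinds of test (2,000 runs; assumed mean stay 30 days, death hazard 0.005 per day, skewed ADL) agrees. At 0, 43, 62 and 88 shared, the log-rank rejected in 4.4%, 1.1%, 0.1% and 0.0% of runs, and the Wilcoxon rank-sum in 5.0%, 1.4%, 0.05% and 0.0%.

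**Power.** Assume that all HAS-positive patients differ from GLIM-only patients by 0.5 SD. The planned contrast then has expected size D = 0.5 × (G − a)/G, which is 0.330, 0.255 and 0.153 at the three non-zero overlaps.
- As written: Φ((D − 1.96 × 0.1384)/true SE) = 71%, 43% and 2%. Simulated t-tests give 69%, 40% and 2%, slightly lower because the mixed GLIM group inflates the pooled SD.
- Same contrast, correct variance: Φ(D/true SE − 1.96). With true SE 0.107, 0.090 and 0.059 this is 87%, 81% and 74%; simulation gives 87%, 80% and 73%, with a null error of about 4.4% to 5.5%.

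**The paired clause.** Each patient has one discharge ADL and one vital status. A shared patient paired with himself always differs by zero, a patient positive on one definition only has no partner, and groups of about 88 and 127 cannot be matched one to one. The clause in 11.2 therefore cannot repair the comparison.

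**The case against.** Five points on the other side deserve weight.

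**The overlap may be far from complete.** This stands. The HAS BMI limit and six-month weight-loss criterion lie inside GLIM's and the aetiological criteria are the same, so substantial overlap is likely. But 10.1 puts an MNA-SF step before the GLIM assessment, and Table 1 in 1.5 lets HAS count grip strength and walking speed where GLIM treats grip as complementary. Both can create HAS-only patients. A reader might take the 88-shared row as the expected case; the documents do not support that.

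**The error is conservative.** True. A reader might infer a risk of false-positive findings, or damage to the primary result. Neither follows: McNemar's test and the estimates within each definition's positive group are unaffected. Conservatism is still a defect when a null result would be read as evidence on the section 1.8 hypothesis.

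**Disjoint classes would be the obvious cure.** Not in general. Comparing patients positive on both with GLIM-only patients drops the HAS-only patients and changes the question in 3.2. Its simulated power is 75%, 80% and 74% in the pooled scenarios, no clear gain over the planned contrast with a correct variance. In an assumed moderate stratum with 10 shared, 40 HAS-only and 40 GLIM-only, it is 29%, against 50% to 51% as written and 61% for the planned contrast with a correct variance.

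**Length of stay.** The absent between-group test might look like the same error. It is a separate and smaller gap in specification: a competing-risk method is named, and the source it cites may describe a test.

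**Mortality may stay weak anyway.** This also stands. In a simulation with an assumed hazard ratio of 3 and 5% deaths, a log-rank on disjoint groups (all HAS-positive versus GLIM-only) reached only 6% to 32% power, against 0% to 12% as written.

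**Conclusion.** The concern holds for the mortality and ADL tests in 11.4.2, and it should be fixed. With 43 to 88 patients shared, a nominal 5% test works at about 1.1% down to almost 0%, and 0.5 SD power falls from 87%–73% to 69%–2%. These figures rest on the planning prevalences, on an assumed overlap, and on an outcome treated as roughly normal although ADL is bounded from 0 to 6.

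For moderate and severe undernutrition taken separately, the documents give neither group sizes nor overlap, and the 10.1 criteria point both ways: a BMI between 17 and 18.5 is moderate under HAS but severe under GLIM, while the HAS albumin criterion has no GLIM counterpart. Any figure for a single stratum is illustrative only.

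This is a secondary objective. The correction makes its tests valid; it does not ensure adequate power for mortality if deaths are few.

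**What to change.** In 11.4.2, keep the HAS-positive versus GLIM-positive contrast that 3.2 asks for, for global, moderate and severe undernutrition, and replace the log-rank and unpaired tests as follows.

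- For each outcome, estimate the difference between the two groups: in-hospital death; cumulative incidence of live discharge with death as a competing event, at a time point named in advance; and ADL at discharge. This also supplies the missing length-of-stay comparison.
- Take the 95% CI and p-value from a bootstrap that resamples patients from the whole cohort, each carrying both classifications and the outcome, or from a variance clustered on the patient. Either way each patient counts once.
- Report the observed HAS × GLIM overlap for global, moderate and severe undernutrition.
- As a supplement, describe outcomes in the mutually exclusive classes (both, GLIM-only, HAS-only, neither) and test only where cells are large enough. If one disjoint contrast is named in advance, state which patients it drops and that it may have less power than the planned analysis.

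The cost is revised SAP wording and slightly more analysis. No new data are needed: sections 9.2 and 9.3 already collect what is required, and 11.2 already promises 95% confidence intervals.

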Secondary evaluation criteria	
 • Prevalences of severe undernutrition according to the HAS and GLIM diagnostic methods; • Morbidity and mortality criteria in the HAS and GLIM moderate and severe undernutrition groups: 
 ○ Duration of hospital stay (days) ; ○ Mortality: proportion and date of occurrence of death among patients included during hospitalisation; ○ Autonomy at discharge: Activities Daily Living score (ADL, Appendix X). • Tools for measuring muscle function : 
 ○ Bioelectrical impedance measurement ; ○ Handgrip ; ○ Walking speed.
Group comparison	Patients hospitalised in short stay and follow-up and rehabilitation care for diabetes-obesity, pneumology, oncology and gastro-nutrition.
Number of subjects needed	260
Expected number of centres	1
Duration of the research	21 months
Statistical analysis of data	Univariate comparisons will use the usual statistical tests after verification of the distribution of the variables (Chi2 or Fisher's test, t-test, anova or their non-parametric equivalents Wilcoxon and Kruskal-Wallis tests). The variables will be compared between the two groups by the appropriate tests according to the type of variables (quantitative or qualitative) and their distribution.
Expected benefits	The results of this study will make it possible to verify whether the GLIM definition increases the prevalence of undernutrition compared to that of the HAS. The use of one or other of the definitions could thus have an impact on the medical and paramedical management of undernutrition. On the other hand, muscle function benefits from different assessment tools, which could lead to a different estimate of the reduction in muscle mass and therefore a different prevalence of undernutrition. The results of our study will help to evaluate this and guide professionals in the choice of tools for assessing muscle function.
Source of funding	Forcilles Hospital-Cognacq-Jay Foundation

Independent Supervisory Committee planned	No
--	----

Table of contents

PROTOCOL VERSION HISTORY.....	3
SUMMARY OF THE RESEARCH.....	4
1 Rationale for the research	10
1.1 Epidemiology and morbidity of undernutrition	10
1.2 Definitions of undernutrition	10
1.3 International consensus on the definition of undernutrition.....	11
1.4 New definition of undernutrition adopted in France.....	11

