10.1 Prevalence of undernutrition

Undernutrition is defined according to the diagnostic methods of the HAS and GLIM:

	Phenotypic criteria			Etiological criteria	
	Weight loss (%)	Low BMI (kg/m ²)	Reduction in muscle mass	Reduction in food intake or absorption	Inflammatory situation
GLIM	> 5% in the last 6 months or > 10% beyond 6 months	< 20	Reduction assessed by a validated measurement technique*.	≤ 50% of food intake > 1 week or any reduction > 2 weeks, or any gastrointestinal conditions or symptoms impacting assimilation or absorption	Acute or certain chronic or malignant conditions
HAS	≥ 5% in 1 month or ≥ 10% in 6 months or loss ≥ 10% from usual weight before onset of disease	< 18,5	Quantified Reduction** (QR)	Same as	Same as

For the GLIM and HAS diagnostic method, the diagnosis of undernutrition is positive if an etiological criterion and a phenotypic criterion are present. The assessment of undernutrition according to GLIM will be preceded by a MNA-SF ([Appendix 4](#)). The methods for measuring the reduction in muscle mass are described in section "**7.2.4. Measurement of muscle function**".

Among patients with undernutrition, severe undernutrition is defined by :

	Moderate undernutrition	Severe undernutrition
GLIM	
 • BMI < 20 kg/m² • Weight loss of 5-10% in the last 6 months or 10-20% beyond 6 months • Mild to moderate reduction in muscle mass 	
 • BMI < 18.5 kg/m² • Weight loss of >10% in the last 6 months or >20% beyond 6 months • Severe reduction in muscle mass
HAS	
 • 17 < BMI < 18.5 kg/m² • Weight loss ≥ 5% in 1 month or ≥ 10% in 6 months or loss ≥ 10% from usual weight before onset of disease • Measurement of albumin by immuno-electrometry or immunoturbidimetry > 30 g/L and < 35 g/L. 	
 • BMI < 17 kg/m² • Weight loss ≥ 10% in 1 month or ≥ 15% in 6 months or loss ≥ 15% from usual weight before onset of disease • Measurement of albumin by immuno-electrodelemetry or immunoturbidimetry < 30 g/L

The prevalence of undernutrition is defined as the proportion of patients with moderate and/or severe undernutrition among the patients included in the study.

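### Comparing HAS and GLIM outcomes grade by grade mixes cut-off position with prognostic value: GLIM-severe will probably look milder, and the direction for moderate is uncertain

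*Combined protocol and SAP*

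**What the plan says.** Section 11.4.2 opens: "Morbidity and mortality will be compared between the HAS and GLIM groups, for moderate and severe undernutrition", using length of stay, mortality and autonomy at discharge. Section 3.2 sets the matching objective, "To compare the morbidity and mortality of moderate and severe undernutrition according to the HAS and GLIM diagnostic criteria", and the synopsis lists "Morbidity and mortality criteria in the HAS and GLIM moderate and severe undernutrition groups". Further down, section 11.4.2 speaks of only two groups: "The mortality rates in the 2 groups will be estimated via the survival curves". Section 2 gives the purpose: the prognostic character of the two definitions is presented as not yet studied.

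The grades come from the second table in section 10.1, which repeats Table 2 of section 1.5. On BMI, HAS-moderate is "17 < BMI < 18.5 kg/m²" and GLIM-severe is "BMI < 18.5 kg/m²". On weight loss, GLIM-severe is "Weight loss of >10% in the last 6 months or >20% beyond 6 months" and HAS-severe is "Weight loss ≥ 10% in 1 month or ≥ 15% in 6 months or loss ≥ 15% from usual weight before onset of disease". HAS also grades on albumin. GLIM also grades on muscle mass, and the table gives no number for a severe reduction.

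Section 11.4.2 plans no cross-table of HAS grade by GLIM grade, no contrast of undernourished with other patients within each definition, and no measure of discrimination.

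**The concern.** Every patient is classified twice, so the two definitions describe the same people and the same outcomes. Where the definitions draw their lines at different depths of depletion, one grade label covers different patients under each. The protocol expects a risk gradient: section 1.1 describes undernutrition as strongly associated with morbidity and mortality. With a gradient, moving a line changes the average outcome on both sides of it, even though nobody's prognosis has changed.

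The risk is in the interpretation. A difference in mortality, stay or ADL between HAS-severe and GLIM-severe would naturally be reported as one definition having more prognostic value than the other, when part or all of it may be cut-off position. This affects a stated secondary objective. The primary prevalence comparison is untouched.

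**Working it through.** The documents give no numerical target for the outcome comparison, so there is no plan figure to reproduce. The check sets the cut-offs side by side and then asks what they imply under stated assumptions.

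**1. Cut-offs (section 10.1).** GLIM-moderate by BMI is what remains of <20 after <18.5 is removed.

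| Criterion | HAS moderate | HAS severe | GLIM moderate | GLIM severe | Consequence |
|---|---|---|---|---|---|
| BMI | 17–18.5 | <17 | 18.5 to <20 | <18.5 | moderate bands disjoint; HAS-moderate is GLIM-severe |
| Loss in 1 month (GLIM's six-month line applies) | ≥5% to <10% | ≥10% | 5–10% | >10% | lines coincide except at the boundary |
| Loss in 6 months | ≥10% to <15% | ≥15% | 5–10% | >10% | above 10% and below 15%: HAS-moderate, GLIM-severe |
| Later loss (HAS: from usual weight) | ≥10% to <15% | ≥15% | 10–20% | >20% | 15–20%: HAS-severe, GLIM-moderate |
| Albumin | 30–35 g/L | <30 g/L | – | – | can raise the HAS grade only |
| Muscle mass | – | – | mild to moderate | severe, no number | can raise the GLIM grade only |

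**2. Does the MNA-SF step before GLIM undo the BMI result?** No. In Annex 4, BMI below 19 scores 0 of 3, so the highest possible total is 14 − 3 = 11. That is still in the at-risk range of 8 to 11. A patient graded on weight loss alone is less certain, because the MNA-SF item covers only 3 months.

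**3. BMI illustration.** Assumed mortality is 5%, 8% and 15% in BMI 18.5–20, 17–18.5 and <17.

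- Moderate: HAS 8%, GLIM 5%.
- Severe: HAS 15%. GLIM with equal bands is (8 + 15)/2 = 11.5%; with band sizes 3:2:1 it is (2×8 + 1×15)/3 = 10.3%.

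**4. All modelled criteria together.** Each scenario simulated 2,000,000 patients with the BMI, weight-loss and albumin lines above. Assumptions:

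- BMI is normal (24, SD 5.5), limited to 13–50.
- Percent loss is normal (4, SD 7) minus 0.2×(BMI − 24), limited to 0–40.
- A quarter of losses not beyond 6 months fall within 1 month.
- An aetiological criterion is present in 80%.
- Albumin, where used, is normal with mean 35 (SD 5 in C and D, 6 in E and F).
- Log odds of an event = −3 + b1·max(22 − BMI, 0) + b2·loss + b3·max(35 − albumin, 0).

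Muscle mass and the MNA-SF were not modelled. Entries are mean risk in %, HAS v GLIM.

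| Scenario (b1, b2, b3) | Severe | Moderate | Grades pooled |
|---|---|---|---|
| A. BMI and loss within 6 months only (0.15, 0.06, 0) | 16.15 v 13.78 | 9.75 v 7.66 | 12.94 v 11.13 |
| B. As A, flat risk (0, 0, 0) | 4.74 v 4.74 | 4.74 v 4.74 | 4.74 v 4.74 |
| C. Albumin rule added, 30% of loss beyond 6 months (0.15, 0.06, 0) | 15.57 v 14.30 | 9.97 v 8.34 | 13.18 v 11.56 |
| D. As C, albumin prognostic (0.15, 0.06, 0.15) | 22.24 v 19.00 | 11.47 v 11.69 | 17.65 v 15.65 |
| E. Albumin strong, others weak, 30% late loss (0.05, 0.03, 0.2) | 16.68 v 13.52 | 8.07 v 11.44 | 13.20 v 12.57 |
| F. Albumin dominant, 30% late loss (0.02, 0.01, 0.25) | 16.18 v 12.55 | 6.93 v 11.84 | 12.45 v 12.22 |
| G. All loss beyond 6 months, no albumin rule (0.15, 0.06, 0) | 17.27 v 16.42 | 10.55 v 10.19 | 13.80 v 13.00 |
| H. As G, risk from loss only (0, 0.1, 0) | 14.50 v 11.02 | 12.46 v 13.59 | 13.45 v 12.43 |

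With a gradient, GLIM-severe is lower by 0.85 (G) to 3.63 (F) points. GLIM-moderate runs from 2.09 points lower (A) to 4.91 higher (F). With flat risk nothing moves.

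**5. Pooling the grades.** Section 11.1 expects prevalences of 34% and 49%. With 260 patients that is 0.34×260 ≈ 88 and 0.49×260 ≈ 127. If HAS cases are nested in GLIM cases (an assumption), the GLIM group is the HAS group plus about 39 patients below the HAS lines. In the pooled column GLIM is lower in every gradient scenario, by 0.23 (F) to 2.00 (D) points.

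**The case against.** The strongest reply is that the two scales are not simply shifted. A reader might infer from the BMI rows that all GLIM lines sit above the HAS lines, so that GLIM-severe is HAS-severe diluted with HAS-moderate patients. The table does not support that. One-month loss lines essentially coincide, late loss and albumin run the other way, and muscle mass grades severity only in GLIM, without a number. This stands, and it limits what can be said about direction.

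A reader might also infer that both GLIM grades must look less morbid whatever the definitions' prognostic value. That fails too: flat risk gives no effect, and the moderate grade reversed in four of the seven gradient scenarios (D, E, F and H). Nor is a shorter stay under GLIM assured, because death ends a stay early, which is why the plan uses competing risks.

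The BMI illustration rests on assumed risks and on the criterion with the clearest shift. The documents give no BMI distribution, and one recruiting service is diabetology-obesity, so BMI may drive few grades. The sizes are therefore indicative only.

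The two-groups wording, and the synopsis objective that names no grades, leave room for a pooled analysis. That does not rescue the contrast, because step 5 shows the same confounding in another form.

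Finally, outcomes under each label are legitimate description and serve a stated objective. This stands: the summaries should stay.

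**Conclusion.** The concern holds in a limited form. The same-grade HAS–GLIM contrasts mix cut-off position with prognostic value, and section 11.4.2 plans nothing that separates them. This follows from the cut-offs in section 10.1 together with one condition, that risk rises with depletion.

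The expected result is that GLIM-severe looks milder. That was consistent across the gradient scenarios, but all of them use assumed distributions and slopes and leave out muscle mass and the MNA-SF. The direction for moderate is uncertain and depends on which criterion carries the risk. Neither a uniform ordering of the two scales nor a guaranteed advantage for GLIM in both grades is supported. An unpredictable sign makes the contrast no easier to read as prognostic value.

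**What to change.** In section 11.4.2:

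- Keep length of stay, mortality and ADL by grade under each definition as description, without same-grade HAS v GLIM tests.
- For the comparison, score each definition as none, moderate or severe over all included patients. Compare how well the two scales rank in-hospital death and discharge, treated as competing events, and discharge ADL among survivors. Report the difference in concordance with a confidence interval from bootstrapping patients. Resampling patients respects the fact that both scores come from the same people, which the planned log-rank comparison does not.
- Show the 3×3 table of HAS grade by GLIM grade with outcomes in each cell.
- Before grading, write down what counts as a severe reduction in muscle mass, and how HAS severity is assigned when albumin is missing. Section 9.2 collects albumin only where applicable, and section 7.2.3 describes it as usual in at-risk patients.

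The cost is plan wording and a bootstrap; sections 9.2 and 9.3 already collect the variables. There are three drawbacks. Concordance is less familiar to clinicians than two curves. Some cells will be small: under the nesting assumption about 133 of 260 patients (260 − 127) are none on both scales, which leaves about 127 for the rest of the table. And the concordance of a three-level scale still depends partly on its cut-offs, so the cross-table should be read beside it.
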